7.2 Assessing and Recording Adverse Events

An AE is defined as any untoward medical occurrence in a patient or clinical investigation subject administered a pharmaceutical product and which does not necessarily have to have a causal relationship with this treatment. An AE can therefore be any unfavourable and unintended sign (including an abnormal laboratory finding, for example), symptom, or disease temporally associated with the use of a medicinal product or protocol-specified procedure, whether or not considered related to the medicinal product or protocol-specified procedure. Any worsening (i.e., any clinically significant adverse change in frequency and/or intensity) of a preexisting condition that is temporally associated with the use of the Sponsor's product, is also an AE.

Changes resulting from normal growth and development that do not vary significantly in frequency or severity from expected levels are not to be considered AEs. Examples of this may include, but are not limited to, teething, typical crying in infants and children and onset of menses or menopause occurring at a physiologically appropriate time.

Sponsor's product includes any pharmaceutical product, biological product, device, diagnostic agent or protocol-specified procedure, whether investigational (including placebo or active comparator medication) or marketed, manufactured by, licensed by, provided by or distributed by the Sponsor for human use.

AEs may occur during clinical trials, or as prescribed in clinical practice, from overdose (whether accidental or intentional), from abuse and from withdrawal.

Progression of the cancer under study is not considered an AE.

All AEs that occur after the consent form is signed but before randomization must be reported by the investigator if they cause the subject to be excluded from the trial, or are the result of a protocol-specified intervention, including but not limited to washout or discontinuation of usual therapy, diet, placebo treatment or a procedure.

From the time of randomization through 30 days following cessation of treatment, all AEs must be reported by the investigator. Such events will be recorded at each examination on the AE CRFs/worksheets. The reporting timeframe for AEs meeting any serious criteria is described in Section 7.2.3.1. The investigator will make every attempt to follow all subjects with nonserious AEs for outcome.

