7.2.3 Immediate Reporting of Adverse Events to the Sponsor

7.2.3.1 Serious Adverse Events

A SAE is any AE occurring at any dose or during any use of Sponsor's product that:

- Results in death;
- Is life threatening;
- Results in persistent or significant disability/incapacity;
- Results in or prolongs an existing inpatient hospitalization;
- Is a congenital anomaly/birth defect;
- Is an other important medical event.

Note: In addition to the above criteria, AEs meeting either of the below criteria, although not serious per ICH definition, are reportable to the Sponsor in the same timeframe as SAEs to meet certain local requirements. Therefore, these events are considered serious by the Sponsor for collection purposes.

- Is a new cancer (that is not a condition of the study);
- Is associated with an overdose.

Refer to [Table 15](#) for additional details regarding each of the above criteria.

For the time period beginning when the consent form is signed until randomization, any SAE, or follow up to a SAE, including death due to any cause other than progression of the cancer under study (reference Section 7.2.3.3 for additional details), that occurs to any subject must be reported within 24 hours to the Sponsor if it causes the subject to be excluded from the trial, or is the result of a protocol-specified intervention, including but not limited to washout or discontinuation of usual therapy, diet, placebo treatment or a procedure.

For the time period beginning at randomization through 90 days following cessation of treatment, or 30 days following cessation of treatment if the subject initiates new anticancer therapy, whichever is earlier, any SAE, or follow up to a SAE, including death due to any cause other than progression of the cancer under study (reference Section 7.2.3.3 for additional details), whether or not related to the Sponsor's product, must be reported within 24 hours to the Sponsor either by electronic media or paper. Electronic reporting procedures can be found in the EDC data entry guidelines. Paper reporting procedures can be found in the Investigator Trial File Binder (or equivalent)

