8.2.5.1.2 Overall Survival (OS)

The nonparametric Kaplan-Meier method will be used to estimate the survival curves. The treatment difference in survival will be assessed by the stratified log-rank test. A stratified Cox proportional hazard model with Efron's method of tie handling will be used to assess the magnitude of the treatment difference (i.e., the hazard ratio). The hazard ratio and its 95% CI from the stratified Cox model with a single treatment covariate will be reported. The same stratification factors used for randomization (see Section 5.4) will be used as the stratification factors in both the stratified log-rank test and the stratified Cox model for the analyses in all subjects and in subjects with PD-L1 CPS 1. For analyses in the PD-L1 CPS 20 subgroup, HPV status and ECOG status will be used as the stratification factors. In the event that there are low event counts (<5) in one or more strata, for the analysis purpose, strata will be combined to ensure sufficient number of events in each stratum. The order of stratification factors to combine strata over is the same as specified for PFS analysis.

Since subjects in the standard therapy arm are expected to discontinue treatment earlier compared to subjects in the pembrolizumab arms, and they may switch to another anti-PD-1 treatment following confirmation of progressive disease, adjustment for the effect of crossover on OS may be performed based on recognized methods, e.g. the Rank Preserving Structural Failure Time model proposed by Robins and Tsiatis (1989) [55], two stage model, etc., based

on an examination of the appropriateness of the data to the assumptions required by the methods.

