8.2.5.2 Statistical Methods for Safety Analyses

Safety and tolerability will be assessed by clinical review of all relevant parameters including AEs, laboratory tests, vital signs, and ECG measurements.

The analysis of safety results will follow a tiered approach (Table 21). The tiers differ with respect to the analyses that will be performed. Safety parameters or adverse experiences of special interest that are identified *a priori* constitute "Tier 1" safety endpoints that will be subject to inferential testing for statistical significance with p-values and 95% confidence intervals provided for between-group comparisons. Other safety parameters will be considered Tier 2 or Tier 3. Tier 2 parameters will be assessed via point estimates with 95% confidence intervals provided for between-group comparisons; only point estimates by treatment group are provided for Tier 3 safety parameters.

Adverse experiences (specific terms as well as system organ class terms) and predefined limits of change in laboratory, vital signs, and ECG parameters that are not pre-specified as Tier-1 endpoints will be classified as belonging to "Tier 2" or "Tier 3," based on the number of events observed. Membership in Tier 2 requires that at least 4 subjects in any treatment group exhibit the event; all other adverse experiences and predefined limits of change will belong to Tier 3.

The threshold of at least 4 events was chosen because the 95% confidence interval for the between-group difference in percent incidence will always include zero when treatment groups of equal size each have less than 4 events and thus would add little to the interpretation of potentially meaningful differences. Because many 95% confidence intervals may be provided without adjustment for multiplicity, the confidence intervals should be regarded as a helpful descriptive measure to be used in review, not a formal method for assessing the statistical significance of the between-group differences in adverse experiences and predefined limits of change.

Continuous measures such as changes from baseline in laboratory, vital signs, and ECG parameters that are not pre-specified as Tier-1 endpoints will be considered Tier 3 safety parameters. Summary statistics for baseline, on-treatment, and change from baseline values will be provided by treatment group in table format.

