For this protocol, there are no Tier 1 events. Adverse experiences (specific terms as well as system organ class terms), consisting of the percentage of subjects with any AE, any drug-related AE, any Grade 3-5 AE, any serious AE, any AE which is both drug-related and Grade 3-5, any AE which is both serious and drug-related, dose modification due to AE, and who discontinued due to an AE, and death that are not pre-specified as Tier-1 endpoints will be classified as belonging to "Tier 2" or "Tier 3," based on the number of events observed. Membership in Tier 2 requires that at least 4 subjects in any treatment group exhibit the event; all other adverse experiences will belong to Tier 3.

Table 21 Analysis Strategy for Safety Parameters

Safety Tier	Safety Endpoint	p-Value	95% CI for Treatment Comparison	Descriptive Statistics
Tier 2	Any AE		X	X
	Any Grade 3-5 AE		X	X
	Any Serious AE		X	X
	Any Drug-Related AE		X	X
	Any Serious and Drug-Related AE		X	X
	Any Grade 3-5 and Drug-Related AE		X	X
	Dose Modification due to AE		X	X
	Discontinuation due to AE		X	X
	Death		X	X
	Specific AEs, SOCs (including ≥ 4 of subjects in one of the treatment groups)		X	X
Tier 3	Specific AEs, SOCs (incidence < 4 of subjects in all of the treatment groups)			X
	Change from Baseline Results (Labs, ECGs, Vital Signs)			X

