8.2.11 Extent of Exposure

Extent of Exposure for a subject is defined as number of cycles in which the subject receives the study medication infusion. Summary statistics will be provided on Extent of Exposure for ASaT population.

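### Tier 2 safety contrasts use crude percentages although time at risk is expected to differ by arm; add common-window and period-split exposure-adjusted summaries

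*Combined protocol and SAP*

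**What the plan says.** - **Measure.** Section 8.2.5.2 classifies adverse experiences "consisting of the percentage of subjects with any AE, any drug-related AE, any Grade 3-5 AE, any serious AE", with further categories of the same kind. Table 21 repeats them.
- **Contrast.** "Tier 2 parameters will be assessed via point estimates with 95% confidence intervals provided for between-group comparisons". The scale is the difference in percent incidence. The plan justifies its threshold of 4 subjects by noting that the interval for this difference "will always include zero when treatment groups of equal size each have less than 4 events".
- **Status.** There are no Tier 1 events, and the intervals are described as "not a formal method for assessing the statistical significance of the between-group differences in adverse experiences".
- **Collection window.** Section 7.2: "From the time of randomization through 30 days following cessation of treatment, all AEs must be reported by the investigator". For serious events, Section 7.2.3.1 runs "through 90 days following cessation of treatment, or 30 days following cessation of treatment if the subject initiates new anticancer therapy", whichever is earlier.
- **Expected exposure.** Section 8.2.5.1.2, discussing crossover, says that "subjects in the standard therapy arm are expected to discontinue treatment earlier compared to subjects in the pembrolizumab arms". Section 5.8.1.1 lets only the pembrolizumab arms be treated past a first verified progression. Section 5.8.1 caps pembrolizumab at 24 months.
- **Exposure analysis.** Section 8.2.11: "Extent of Exposure for a subject is defined as number of cycles in which the subject receives the study medication infusion". Only summary statistics are planned.

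Section 8 specifies no exposure-adjusted rate, time-to-first-event analysis or common observation window for safety.

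**The concern.** When the observation window lengthens with treatment, the percentage of subjects with at least one event rises with time on treatment even if the underlying event rate is the same. The plan expects treatment duration to differ by arm, so a crude difference mixes the regimens' toxicity with how long each was given and watched.

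Safety and tolerability of both pembrolizumab regimens is the first secondary objective (Section 3.2), and Section 4.3 argues from a tolerability advantage over the control regimen. Readers will use the Tier 2 intervals to judge that advantage. If the control arm stops earlier, as expected, crude percentages work against pembrolizumab and could hide a real difference.

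**Working it through.** **Inputs from the documents**
- 825 subjects at 1:1:1, so 275 per arm (8.2.7).
- 30 days of collection after the last dose: w = 30/30.44 = 0.99 month (7.2).
- 24-month cap for pembrolizumab only (5.8.1).
- At most 6 three-week chemotherapy cycles (5.2): 18 weeks, so a = 126/30.44 = 4.14 months.
- PFS median 6 months in control and hazard ratio 0.6 in all subjects (8.2.7).

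**Assumptions (not in the documents)**
- Exponential time on treatment with mean 4 months in control and 6 or 8 months with pembrolizumab; as a third case, the plan's PFS inputs serve as a proxy for time on treatment.
- An AE hazard of 0.05 per month, identical in both arms.

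**Step 1: reproduce the plan's figures.** The safety section has no power statement, so I checked the PFS inputs and the Tier 2 threshold.
- Expected PFS events per arm = 275 × the average over 21 months of uniform accrual of λ/(λ+g) × [1 − exp(−(λ+g)t)], with λ = ln2/6 (control) or 0.6 × ln2/6, and g = −ln(0.95)/12 for 5% yearly dropout. The two-arm sum is 423.2 at 30 months (stated 423) and 473.8 at 38 months (stated 474).
- Miettinen-Nurminen 95% CI at 275 per arm: 3 versus 0 events gives −0.3 to 3.2 points (includes zero); 4 versus 0 gives 0.06 to 3.7 points (excludes it). This agrees with the plan's threshold and with a crude risk difference as the contrast.

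**Step 2: constant hazard.** Crude incidence = 1 − E[exp(−h(T+w))], where T is time on treatment with rate λ = 1/mean.
- Control, mean 4 months: 1 − exp(−0.05 × 0.99) × 0.25/(0.25 + 0.05) = 1 − 0.952 × 0.833 = 20.7%.
- Pembrolizumab, mean 6 months, capped at c = 24: E[exp(−hT)] = λ/(λ+h) × (1 − exp(−(λ+h)c)) + exp(−(λ+h)c) = 0.769 × 0.994 + 0.006 = 0.771, so 1 − 0.952 × 0.771 = 26.7%.

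**Step 3: front-loaded hazard.** Take 0.05 per month up to a, then h2 = 0.01 or 0. Split at t0 = a − w = 3.15 months. For control with h2 = 0.01:
- Stops before t0: 0.952 × 0.25/0.30 × (1 − exp(−0.30 × 3.15)) = 0.485.
- Stops after t0: exp(−0.05 × 4.14) × exp(−0.25 × 3.15) × 0.25/0.26 = 0.355.
- Incidence = 1 − 0.485 − 0.355 = 15.9% (unrounded terms).

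The last column is the ratio (pembrolizumab to control) of first-event rates, each rate being incidence divided by expected person-time to first event or end of window. For 4 versus 6 months and h2 = 0.01: (18.3/5.79)/(15.9/4.32) = 3.17/3.69 = 0.86 per 100 person-months.

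| Exposure (control v pembrolizumab) | Hazard after 18 weeks | Crude % | Difference (95% CI half-width) | Overall rate ratio |
|---|---|---|---|---|
| mean 4 v 6 months | 0.05 | 20.7 v 26.7 | 6.0 (7.1) | 1.00 |
| mean 4 v 8 months | 0.05 | 20.7 v 31.6 | 10.9 (7.3) | 1.00 |
| PFS proxy | 0.05 | 33.6 v 42.4 | 8.9 (8.1) | 1.00 |
| mean 4 v 6 months | 0.01 | 15.9 v 18.3 | 2.4 (6.3) | 0.86 |
| mean 4 v 8 months | 0.01 | 15.9 v 20.2 | 4.2 (6.4) | 0.77 |
| mean 4 v 6 months | 0 | 14.5 v 15.7 | 1.2 (6.0) | 0.80 |
| mean 4 v 8 months | 0 | 14.5 v 16.3 | 1.8 (6.0) | 0.67 |

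The true hazards are equal in every row, so the correct rate ratio is 1.00 throughout.

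**Step 4: sensitivity, constant hazard, PFS proxy.** Mean time at risk is 9.6 versus 12.7 months.
- Over hazards of 0.005 to 0.20 per month the artefact is 1.4 to 10.6 points.
- With a 6-month median in both arms it is −0.6 to 0.0 points.
- If the pembrolizumab hazard is truly 30% lower, the crude difference is −0.7, −0.4 and +0.5 points at control hazards of 0.02, 0.05 and 0.10, so the advantage nearly disappears.

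**The case against.** The strongest reply is that nothing here is an error. The percentage with an event is a legitimate measure of risk over the regimen as given. The intervals are declared descriptive, no safety p-value or decision rule depends on them, and exposure is summarised in the same ASaT population. Supplementary analyses could sit in the sSAP, which is not among the documents. All of that stands. It limits the point to interpretation, and Sections 8.0 and 8.2.5 do not promise this analysis.

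A second reply is that a constant hazard suits this trial poorly, because platinum and 5-FU stop after 6 cycles. That also stands. It cuts the artefact to about 1 to 4 points, inside the CI half-width in those rows. It also shows that a single overall exposure-adjusted rate would be biased the other way, giving the longer-treated arm a false 14 to 23% advantage when the hazard falls to 0.01.

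Three stronger readings are tempting and not supported:
- *The crude tables flatter pembrolizumab.* Under the plan's own expectation of earlier stopping in control, the exposure effect runs against pembrolizumab.
- *Unequal visit schedules add to the time-at-risk problem.* AE review is marked on Days 1, 8 and 15 in control and once per cycle in the pembrolizumab arms (Section 6.1), so 18 against 6 reviews over 6 cycles. That concerns detection, not time at risk. It would tend to raise control counts, opposite to the exposure effect, and the documents give no way to size it. All AEs in the window must be reported whatever the visit day, so it matters mainly for asymptomatic laboratory events.
- *Laboratory events could be compared on Day 1 samples alone.* Section 5.2.1.2.4 lets control-arm chemotherapy restart on Day 8 or 15 after a delay, so Day 1 need not mark the same point of treatment in each arm.

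**Conclusion.** The point holds as a modest improvement to a descriptive analysis. Tier 2 differences partly reflect time at risk, because the measure is crude, the window follows treatment, and the plan expects unequal treatment duration.

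The size cannot be fixed from the documents. At an assumed 5% per month, the 4 versus 6 and 4 versus 8 month cases give about 6 to 11 points under a constant hazard and about 1 to 4 points when toxicity falls after 18 weeks. With equal exposure it is close to zero. Categories that nearly every subject experiences would also show less.

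A reader might infer that a Tier 2 interval excluding zero would be an exposure artefact, or that the safety conclusion is invalid. Neither follows: several assumed cases stay within the interval half-width, and no formal inference is made.

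**What to change.** Keep the crude tables. For the Tier 2 summary categories (any AE, Grade 3-5, serious, drug-related, discontinuation due to AE) add, in Section 8.2.5.2 or the sSAP:

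1. Time-to-first-event cumulative incidence by arm, with between-arm differences and 95% CIs at a common early window such as 18 weeks, treating death as a competing event. State how the end of AE collection and treatment stop for other reasons are handled, since the latter precludes discontinuation due to an AE.
2. Exposure-adjusted incidence rates (first events per 100 person-months within the collection window), reported separately up to and after 18 weeks, not as one overall rate.
3. Extent of exposure in months as well as cycles (Section 8.2.11).
4. A note that AE review is weekly in control and three-weekly in the pembrolizumab arms, as a caveat on detection, mainly for asymptomatic laboratory events.

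The cost is extra tables, using AE and dosing data the trial collects anyway, with no change to design, sample size or alpha. The rates still assume a roughly constant hazard within each period.

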8.2.5.3 Statistical Methods for PRO Analyses

The Kaplan-Meier method will be used to estimate the TTD survival curve for each of the global health status/quality of life, pain and swallowing outcomes in each treatment group. A stratified Cox proportional hazard (PH) model with Efron's method of tie handling will be used to assess the magnitude of the treatment difference. Stratification factors used for randomization will be used in the stratified Cox PH model. The hazard ratio, 95% confidence interval, and nominal p-value will be reported.

To assess the treatment effects on the PRO score changes from baseline in the global health status/quality-of-life outcome, a constrained longitudinal data analysis (cLDA) model will be applied, with the PRO score as the response variable, and treatment by time interaction, and stratification factors as covariates. Treatment effect on PRO score change from baseline will be primarily evaluated at Week 15. The differences in the least square mean change from baseline will be reported at the primary analysis time point.

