3.2 Secondary Objective(s) & Hypothesis(es)

(1) **Objective:** To evaluate the safety and tolerability profile of pembrolizumab monotherapy or a combination of pembrolizumab with chemotherapy in all first line R/M HNSCC subjects.

The following secondary objectives will be evaluated in (1) PD-L1 CPS 20, (2) PD-L1 CPS 1 and (3) all subjects for both pembrolizumab in combination with chemotherapy and pembrolizumab monotherapy compared to standard treatment.

(2) **Objective:** To evaluate proportion progression free at 6 months and 12 months per RECIST 1.1 by BICR of first line R/M HNSCC subjects.

(3) **Objective:** To evaluate objective response rate (ORR) per RECIST 1.1 by BICR in first line R/M HNSCC subjects.

(4) **Objective:** To evaluate mean change from baseline in global health status/quality of life in first line R/M HNSCC subjects.

(5) **Objective:** To evaluate TTD in global health status/quality of life, pain and swallowing in first line R/M HNSCC subjects.

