For the global health status/quality of life and function scales, a higher value indicates a better level of function; for symptom scales and items, a higher value indicates increased severity of symptoms. Prior literature indicates that head and neck pain and the ability to swallow are clinically relevant symptom measures in the R/M HNSCC population [48; 49; 50; 51]. Thus, TTD in the pain and swallowing multi-item scales of the EORTC QLQ-H&N35, in addition to TTD and mean change from baseline in global health status/quality-of-life scale of the EORTC QLQ-C30, will be evaluated as secondary objectives.

The EORTC QLQ-C30 and EORTC QLQ-H&N35 are to be completed at various time points as specified in the study Flow Chart, beginning with Cycle 1 until 30 days posttreatment discontinuation.

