5.4 Stratification

Randomization will be stratified according to the following factors:

1. PD-L1 tumor expression as determined by PD-L1 immunohistochemistry (strongly positive vs. not strongly positive)
Note: *Strongly positive* includes those subjects whose tumor expression levels are $\geq 50\%$. *Not strongly positive* includes those subjects whose tumor expression levels are $< 50\%$, or are not able to be determined for any reason.
2. HPV status for oropharynx cancer as determined by p16 immunohistochemistry (IHC) (positive vs. negative); HPV status for subjects without oropharynx cancer (e.g. cancers of the oral cavity, hypopharynx and larynx) is considered HPV negative.

3. Eastern Cooperative Oncology Group (ECOG) Performance Scale (0 vs. 1)

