- x. It is a best practice and strongly recommended that ePROs are administered to randomized subjects prior to drug administration, AE evaluation, and disease status notification. All ePROs are to be performed prior to dosing at Cycle 1, Cycle 2, Cycle 3, Cycle 4 and every 2 cycles thereafter (e.g., Cycle 6, Cycle 8, Cycle 10) up to 1 year from treatment initiation or End of Treatment, whichever occurs first, and at the 30-day Safety Follow-up Visit. If the subject does not complete the ePROs for any reason, the Miss Mode form must be completed to capture the reason the assessment was not performed. The Pain Medication Log should be collected at all scheduled visits from Screening through the Safety Follow-up Visit (see Section 4.2.3.5.3).
- y. This sample should be drawn for planned, exploratory genetic analysis of DNA unless there is either a documented law or regulation prohibiting collection, or unless the IRB/IEC does not approve of the collection.

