8.2.3.3 PRO Endpoints

Global health status/quality-of-life assessment is based on the global health status/quality-of-life scales of the QLQ-C30 (items 29 and 30); pain is based on the pain multi-item scales of the EORTC QLQ-H&N35 (items 31-34), and TTD in swallowing is based on the swallowing multi-item scales of the EORTC QLQ-H&N35 (items 35-38).

TTD is defined as the time from baseline to first onset of PRO deterioration with confirmation (true deterioration). Here, true deterioration in the global health status/quality of life, pain, and swallowing endpoints is defined as a 10 points or greater worsening from baseline for each

multi-item scale [48; 52; 53] and confirmed by a second adjacent 10 or more deterioration from baseline under a right-censoring rule.

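### The time-to-deterioration Cox model names no baseline-score covariate, although the event is measured from that score; the analysis is valid, but its hazard ratio is pulled toward 1 and some power is lost.

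*Combined protocol and SAP*

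**What the plan says.** TTD is a secondary objective (Section 3.2): "To evaluate TTD in global health status/quality of life, pain and swallowing in first line R/M HNSCC subjects". It applies to CPS 20, CPS 1 and all subjects, and to both experimental arms against standard treatment.

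Section 8.2.3.3 makes the event a deterioration "defined as a 10 points or greater worsening from baseline", confirmed at the adjacent assessment. Section 4.2.3.5 gives the direction of the scales. Higher is better for global health, but "for symptom scales and items, a higher value indicates increased severity of symptoms". So the event is a fall for global health and a rise for pain and swallowing.

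Section 8.2.5.3 compares the arms with a stratified Cox model with Efron ties. On adjustment it says: "Stratification factors used for randomization will be used in the stratified Cox PH model". Section 5.4 lists those factors as PD-L1 expression, HPV status and ECOG status; none is a PRO score. On output it says: "The hazard ratio, 95% confidence interval, and nominal p-value will be reported".

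The baseline score is collected. Under the flow chart in 6.1.1, "All ePROs are to be performed prior to dosing at Cycle 1", and the standard-arm chart in 6.1.2 says the same. Section 8.0 adds that the PRO analysis plan is also placed in the supplemental SAP (sSAP), which is not among the documents.

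**The concern.** The observed baseline score is part of the event definition. A subject whose first score was favourable, partly by chance, tends to drift back at later visits and has more room to cross the 10-point line. A subject who starts near the bad end of the scale has little or no room. The score should therefore predict the event in every TTD analysis, in opposite directions for global health and for the two symptom scales.

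In a Cox model, omitting a strong predictor that is independent of treatment brings the treatment hazard ratio closer to 1 than the ratio conditional on that predictor, and weakens the test. The plan reports 3 scales x 3 populations x 2 comparisons = 18 TTD hazard ratios. In the same section, the constrained longitudinal model for mean change takes the PRO score as its response, and a model of that type normally carries baseline in the response vector. The TTD model has no counterpart.

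**Working it through.** **No planned figure to reproduce.** The documents give no event count, effect size, SD or power for TTD. The check is by simulation, fitting each simulated trial with and without the standardized baseline score.

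**Inputs from the plan.** 825 subjects randomized 1:1:1, so 825/3 = 275 per arm; a 10-point threshold confirmed at the adjacent visit; ePROs before Cycles 2, 3, 4, 6, 8 and so on, i.e. weeks 3, 6, 9, 15, 21, ..., 51.

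**Assumed inputs.**
- Simulation 1 (2000 trials per setting): exponential event times, treatment HR 1 or 0.75, baseline log HR per SD of 0, 0.2, 0.4 or 0.6.
- Simulation 2 (1000 trials per setting): a falling 0-100 score in steps of 100/12, baseline mean 60, SD 22, within-patient correlation 0.5 or 0.7, exponential dropout with mean 40 weeks, treatment effect 0 or 3 points at week 15.
- Both use Breslow ties and no strata, simpler than the planned stratified Efron model.

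**Results with a treatment effect (unadjusted -> adjusted).**

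| Setting | HR | SE of log HR | Power, % | Gain, points |
|---|---|---|---|---|
| Sim 1, 0.2 per SD | 0.752 -> 0.749 | 0.1388 -> 0.1390 | 53.4 -> 54.5 | 1.1 |
| Sim 1, 0.4 per SD | 0.759 -> 0.749 | 0.1378 -> 0.1381 | 51.2 -> 55.1 | 3.9 |
| Sim 1, 0.6 per SD | 0.770 -> 0.747 | 0.1368 -> 0.1372 | 47.6 -> 57.1 | 9.5 |
| Sim 2, correlation 0.5 | 0.789 -> 0.774 | 0.1527 -> 0.1532 | 31.7 -> 40.0 | 8.3 |
| Sim 2, correlation 0.7 | 0.713 -> 0.705 | 0.1667 -> 0.1670 | 52.5 -> 55.8 | 3.3 |

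With a baseline that predicts nothing, Simulation 1 gave 54.5 -> 55.3, a difference of 0.8 points. The 1.1 points at 0.2 per SD is therefore close to simulation noise.

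**Where the gain comes from.** The SE rises slightly (0.1532/0.1527 = 1.003). The estimate moves away from 1. At 0.6 per SD, z = ln(0.770)/0.1368 = -1.91 unadjusted and ln(0.747)/0.1372 = -2.13 adjusted. The squared ratio is 1.24, like 24% more information for the test. The same calculation gives 1.03, 1.09, 1.16 and 1.06 for the other rows, in table order. A separate simulation with 137 or 275 per arm and reliability 0.6 or 0.8 gave 1.03 to 1.26.

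**Is baseline prognostic under this event definition?** In Simulation 2 its strength was not set but resulted from the definition. With a treatment effect, the fitted log HR was 0.85 per SD (correlation 0.5) and 0.64 (correlation 0.7), i.e. hazard ratios of exp(0.85) = 2.3 and exp(0.64) = 1.9.

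**Validity with no treatment effect.** The unadjusted two-sided 5% test rejected in 4.6% to 5.7% of trials (Simulation 1) and 3.2% to 4.4% (Simulation 2). Mean HR was 0.995 to 1.003. In Simulation 1 the empirical SD of the log HR (0.130 to 0.133) matched the model SE (0.130 to 0.132).

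**Chance imbalance.** The SE of the standardized baseline difference is sqrt(2/275) = 0.085, so 95% of randomizations fall within 1.96 x 0.085 = 0.167 SD. At 0.2 to 0.6 per SD this moves the unadjusted HR by a factor of up to exp(0.033) = 1.03 to exp(0.100) = 1.11; at 0.85 per SD, exp(0.142) = 1.15. In CPS 20 (50% prevalence, about 137 per arm) the SE is sqrt(2/137.5) = 0.121. These shifts are random and centred on no shift, and the reported SE already contains them.

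**The case against.** The case for leaving the model alone has several parts.

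- **Validity and importance.** The planned test holds its level. TTD has no alpha in Section 8.2.6, no power claim, and nominal p-values that Section 8.2.5 does not treat as formal tests. This stands; it limits the importance of the point but does not remove the gain.
- **Estimand.** The unadjusted HR is marginal to baseline and matches the Kaplan-Meier curves; the adjusted HR is conditional on baseline. This stands, and is met by pre-specifying which is primary and reporting both.
- **Silence.** Sections 8.2.5.1.1 and 8.2.5.1.2 state that the PFS and OS models carry treatment as the sole covariate; 8.2.5.3 does not say so for TTD, and the sSAP may add terms. So a reader might infer that the full plan excludes the baseline score, but the documents show only that 8.2.5.3 names no such term.
- **Linearity.** A subject with under 10 points of room cannot have an event, and a linear term captures this threshold only roughly. This stands, but a linear term still recovered power in Simulation 2, which had scale limits.

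Two stronger readings are tempting and wrong. A reader might infer that omission widens the confidence interval on the log HR scale; the SEs above show it does not. A reader might also infer that chance baseline imbalance biases the comparison; under randomization it does not, and the interval covers it.

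**Conclusion.** The point holds as an efficiency and specification matter. Section 8.2.5.3 names no baseline-score covariate for an event measured from that score. The cost is attenuation of the HR toward 1 (for example 0.774 to 0.789, or 0.747 to 0.770) and a power loss of 1.1 to 9.5 percentage points, the low end being negligible.

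Every size rests on assumed SD, correlation, dropout, effect size and prognostic strength. Simulation 2 covers a falling scale only; pain and swallowing could differ if many subjects start at an extreme of those scales. No primary conclusion of the trial depends on the point.

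**What to change.** In 8.2.5.3, and in the same terms in the sSAP, specify for all three TTD endpoints a stratified Cox PH model (randomization strata and Efron ties as now) with treatment and the baseline score of the scale analysed as a continuous covariate. Keep the Kaplan-Meier curves and report the unadjusted stratified HR as supportive. State that the adjusted HR is conditional on baseline.

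State also that subjects without a baseline score do not enter the adjusted model. Section 8.2.4.3 admits subjects to the PRO set on any one assessment, so such subjects are possible. Say how subjects with less than 10 points of room to worsen are handled.

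The cost is one covariate and a few sentences, with no new data. If TTD results have already been seen, label the adjusted analysis as added afterwards.
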